4.5 Efficacy Evaluations

4.5.1 Diagnostic Tests, Scales, Measures, etc.

Methods and timing the measures that will be used to assess efficacy

| Study Measures and Timing | | | | | |
|---------------------------|------------------|----------------------------------|-------------------|--|--|
| Measure | Source | Time to Complete (minutes) | Timing (months) | | |
| ADHD PGI (primary) | Parent | 5 | 0 | | |
| VPRS (primary) | Parent | 5 | 0, 3-5, 6-8, 9-12 | | |
| VTRS (primary) | Epic records | n/a (usual care) | n/a (usual care) | | |
| GAS (primary) | Parent | 1-2 | 3-5, 6-8, 9-12 | | |
| Engagement (M) | Parent | 3-5 | 3 | | |
| Medications (M) | her | 0 | 1-9-12 | | |
| SACA (M) | Parent | 10 | 9-12 | | |
| PROs (secondary) | | | | | |
| School performance | Child, Parent | 3-5 | 0,9-12 | | |
| Student engagement | Child, Parent | 3-5 | 0,9-12 | | |
| Peer relationships | Child, Parent | 3-5 | 0,9-12 | | |
| Family belonging | Child, Parent | 3-5 | 0,9-12 | | |
| Teacher connectedness | Child, Parent | 3-5 | 0,9-12 | | |
| PFCC Questionnaire | Parent | 10 | 9-12, 9.5-12 | | |
| Satisfaction Survey | Parent | 10 | 9+ | | |

| Qualitative Interview | Parent | 30 | 9+ | | |
|---|--------|----|----|--|--|
| School performance, student engagement, and teacher connectedness are | | | | | |
| Healthy Pathways scales; peer relationships and family belonging are PROMIS scales (M) denotes a mediator | | | | | |

4.6 Safety Evaluation

Subject safety will be monitored by adverse events, and follow-up surveys. The research team will query participants at every follow up visit to determine if personal health information has been disclosed.

5 STATISTICAL CONSIDERATIONS

5.1 Primary Endpoint

The primary endpoints will be the change in ADHD Symptoms (as measured by the VPRS and VTRS) and the change in Goal Attainment (as determined by the treatment goals of the patients and their families) between baseline and the 3-5, 6-8, and 9-12-month points.

5.2 Secondary Endpoints

Secondary endpoints will include the following:

- The change in PROs, which parents of children with ADHD and teachers have identified as most important: school performance, student engagement, peer relationships, family belonging, and teacher connectedness.
- To evaluate consistency of PFCC measure that was developed for purposes of this study.
- Parent satisfaction in the intervention group with the services rendered by their care manager.
- Parent outcome experience and feedback in the intervention group with care management.

5.3 Statistical Methods

5.3.1 Baseline Data

Based on intake data across the CHOP Care Network, the study team expects a racial and ethnic breakdown to be representative of patient population seen over the past two years: 59% white, 31% black or African American, and 5% Hispanic. The actual demographic distribution of enrolled participants may differ slightly. The study team also expects that the gender distribution will reflect the gender distribution of children with ADHD in the CHOP Care Network: 72% male, 28% female.

5.3.2 Efficacy Analysis

Primary analyses will be based on an intention to treat approach and will include all subjects as randomized. We will follow usual guidelines for reporting results (CONSORT)

(CONSORT Group, 2010), and will report all outcomes in both absolute (how much change) and relative terms (percentage change). In sensitivity analyses to examine the impact of preference and treatment intensity, we will look at the effects of the intervention stratified by baseline preferences and intervention dosage (frequency of interaction with the portal/CM).

The primary endpoints will be the change in ADHD Symptoms (as measured by the VPRS and VTRS) and the change in Goal Attainment (as determined by the treatment goals of the patients and their families) between baseline and the 3-5, 6-8, and 9-12-month points.

• Secondary endpoints will include the change in PROs, which parents of children with ADHD and teachers have identified as most important: school performance, student engagement, peer relationships, family belonging, and teacher connectedness. In addition, PFCC measure will be examined for internal consistency with test-retest reliability. The satisfaction survey will measure how satisfied parents in the intervention arm were with the services provided by their care manager. The qualitative interview will evaluate outcome experience and feedback in the intervention group with care management.

5.4 Safety Analysis

AE incidence will be summarized along with the corresponding exact binomial 95% two-sided confidence intervals.

5.5 Sample Size and [name]

Aim 1: The investigative team assumed that there will be 240 evaluable children parent-child dyads (from 300 enrolled), and that these will be divided 1:1 across the two groups. From these assumptions, power analyses we conducted based on simulations, in which two groups of 120 children were generated, followed over 3 time periods (totaling 9-12 months), where the measurements were correlated from baseline to 6-8 months (corr=0.8) and from baseline to 9-12 months (r=0.6). The investigative team assumed that the true differences between treatment groups was a score of 5.0 units over time. Once a dataset was simulated, a marginal model for longitudinal data was applied (GEE with a first order auto-regressive working correlation structure and robust variance estimates). For comparing the effect of the intervention, power of 0.87 was found to detect a difference of 2.5 points along the Vanderbilt score (assuming a standard deviation of 6 points, and a difference of 2 points assuming a standard deviation of 5). These good levels of power are achievable with the longitudinal design.

Aim 2: For the outcomes of initiation and adherence, binary outcomes were assumed and performed analyses using the PASS 13 software (Hintze, 2011). For the purposes of this study, the ADHD PGI will be used to determine the level of initiation and adherence. Initiation is defined as starting a treatment plan for which one has moderate to greater preference. Adherence is defined as the continuation of treatment through month 9-12. Assuming that the tier 1 group of 120 children experiences a 50% rate of initiation and adherence, power would be about 0.89 to detect an increase in that rate among the tier 2 group to 70% and would be greater than 0.98 to detect an increase to 75%.

Aim 3: Again, the investigative team resorted to simulation to determine the power to detect an interaction of group and intervention. For this analysis, it was assumed that 50% of the children will come from inner city practices and the other 50% for non-urban locations. The investigative team also assumed further that the electronic intervention would work less well than the in-person intervention among inner-city children, but that it would work equally well among the suburban children. (1) [name] is greater than 0.90 if the suburban tier 2, suburban tier 1, and urban tier 2 practices improve by 7 points on the symptoms scale (assuming a standard deviation of 6), and urban tier 1 practices improved by only 2.5 points, a clinically meaningful difference.

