Aim #3: To explore individual, family, and community factors that moderate treatment effects, the same longitudinal data models supported estimates of effect modification by means of 3-way interaction terms of time-by-treatment-by effect modifier as well as subgroup analyses. Factors of importance explored in this aim included parent education level (high school vs. less than high school), race/ethnicity, medication status, and neighborhood variables (median income, metropolitan status). To obtain the community level variables, each participant was geocoded via street address, city and ZIP code. American Community Survey Census tract level information including median income, percent high school graduation, population density, and percent poverty were linked to participant tracts. Urbanicity was defined as home residence in Philadelphia County (urban) vs suburban county. Bivariate differences between intervention status and the above factors were assessed utilizing Chi-square tests for categorical characteristics, and t-tests/Wilcoxon rank sum tests for continuous characteristics.

Moderation models and stratified models were conducted separately for each

outcome, following the same modeling strategy in Aim 1 with GEE (marginal) models accounting for clinic site and seasonality.

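### The stated powers for Aim 1 (0.87) and the Aim 3 interaction (above 0.90) conflict under any common set-up, and the protocol gives no separate set-up for Aim 3

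*Protocol*

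**What the plan says.** All the power statements are in Protocol 5.5.

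- **Aim 1.** 240 evaluable dyads out of 300 enrolled, 120 per arm. Data were simulated with correlations of 0.8 (baseline to 6-8 months) and 0.6 (baseline to 9-12 months) and analysed by GEE with an AR(1) working correlation and robust variance. The result: "power of 0.87 was found to detect a difference of 2.5 points along the Vanderbilt score", with SD 6. The same power is attached to 2 points with SD 5. The paragraph also states: "The investigative team assumed that the true differences between treatment groups was a score of 5.0 units over time".
- **Aim 3.** "Again, the investigative team resorted to simulation to determine the power to detect an interaction of group and intervention". The split is that "50% of the children will come from inner city practices and the other 50% for non-urban locations". Power "is greater than 0.90 if the suburban tier 2, suburban tier 1, and urban tier 2 practices improve by 7 points" with SD 6, while "urban tier 1 practices improved by only 2.5 points, a clinically meaningful difference".

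Neither aim states alpha or sidedness. Aim 3 restates no sample size, correlations, model or tested contrast. On the later analysis, the SAP (Aim #3) says that "the same longitudinal data models supported estimates of effect modification by means of 3-way interaction terms", "following the same modeling strategy in Aim 1 with GEE (marginal) models".

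**The concern.** The Aim 3 effect is an interaction: the tier difference in urban children minus the tier difference in suburban children. Cutting the same sample into four cells doubles the standard error relative to the two-arm comparison. An interaction must therefore be twice as large as the main effect to be equally well powered. Here 4.5 points is less than twice 2.5, yet Aim 3 is given the higher power.

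At stake is how null results are read. SAP Aim #2 reports that no primary or secondary outcome differed between the groups, so a reader will look to the planned power to judge what was ruled out. The protocol ranks the moderator test as better powered than the primary comparison. Under a shared set-up the order is the other way round.

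**Working it through.** **Inputs.** From Protocol 5.5: 120 per arm; 2.5 points with SD 6, or 2 points with SD 5; r = 0.6 from baseline to 9-12 months; a 50:50 urban split; SD 6 for Aim 3. Assumed because not stated: two-sided alpha 0.05, and the same 240 children for Aim 3, so 60 per cell. Powers in steps 2 and 3 use the noncentral t distribution.

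**Step 1. Aim 3 contrast.** (7 − 2.5) − (7 − 7) = 4.5 points.

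**Step 2. Reproduce Aim 1, SD taken directly.** SE = SD × √(2/120).
- 2.5 points, SD 6: SE = 0.775, noncentrality 2.5/0.775 = 3.23, power 0.895.
- 2 points, SD 5: SE = 0.645, noncentrality 2/0.645 = 3.10, power 0.870.

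So 0.87 is reproduced for the second pair but not for the first. The standardized effects differ (2.5/6 = 0.417 and 2/5 = 0.400), although the protocol gives them one power.

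**Step 3. Both aims under a common set-up.** For Aim 3, SE = SD × √(4/60). For change from baseline, SD is multiplied by √(2 × (1 − 0.6)) = 0.894, so 6 becomes 5.37 and 5 becomes 4.47.

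| Set-up | Aim 1, 2.5 / SD 6 | Aim 1, 2 / SD 5 | Aim 3, 4.5 / SD 6 |
|---|---|---|---|
| Stated in protocol | 0.87 | 0.87 | above 0.90 |
| SD taken directly | 0.895 | 0.870 | 0.825 |
| Change from baseline, r = 0.6 | 0.949 | 0.932 | 0.899 |
| Simulated GEE, constant effect | 0.949 | 0.937 | 0.897 |
| Simulated GEE, effect growing linearly | 0.950 | 0.935 | 0.899 |

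The GEE rows use AR(1) working correlation, robust variance, three visits and 1,500 runs. The correlation between the last two visits is not given and was assumed to be 0.8. Twelve further simulated pairs (2.5 / SD 6 for Aim 1), with three or four visits and various contrasts, all put Aim 3 below Aim 1. Wherever Aim 3 exceeded 0.90, Aim 1 was 0.944 or more.

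**Step 4. Why the order is fixed.** With a common per-child standard deviation s, the Aim 1 SE is s√(2/120) = 0.1291s and the Aim 3 SE is s√(4/60) = 0.2582s, exactly double. The ratio of noncentralities, Aim 3 to Aim 1, is:
- 4.5 / (2 × 2.5) = 0.90 for the SD 6 pair;
- (4.5/6) / (2 × 2/5) = 0.9375 for the SD 5 pair.

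The correlations and the visit weighting cancel. Both ratios are below 1, so at a common alpha Aim 3 power is always the lower. Conversely, Aim 3 at 0.90 (noncentrality 3.242, normal approximation) implies 3.242/0.90 = 3.602 for Aim 1, power 0.950. For the SD 5 pair it implies 3.242/0.9375 = 3.458, power 0.933.

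**Step 5. The 5.0 units.** At 5.0 points and SD 6 the two-arm noncentrality is 5.0/0.775 = 6.45, and power is above 0.999.

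**The case against.** The strongest reply is that the documents do not impose a shared set-up. Reusing simulation does not mean reusing every input. The SAP describes, in the past tense, the analysis of collected data through a three-way interaction with time. It cannot establish what was simulated when the protocol was written. The wording of the two aims also differs: Aim 1 speaks of a difference in score, Aim 3 of cells that improve. Read literally, a score difference gives 0.870 for Aim 1 (2 points, SD 5), and a change at r = 0.6 gives 0.899 for Aim 3. That is close to the stated pair.

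Much of this stands. A mixed set-up is possible, and the fault would then be missing reporting of the Aim 3 inputs. But the protocol does not say that the contrasts differ, and Protocol 5.1 defines the primary symptom endpoint as change from baseline, which does not favour a score difference for Aim 1 alone. Using all 300 children in Aim 3 only (75 per cell, SD 6 directly) would also give 0.899, but that too is unstated, and Aim 1 plans on 240 evaluable.

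Two other escapes do not help. An urban-only comparison (60 against 60, 4.5 points) has power of about 0.98, but the text names an interaction. If 0.87 belonged to the 5.0 units, the ratio would be 4.5/(2 × 5.0) = 0.45 and Aim 3 power about 0.28, a wider conflict.

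It is also fair to say that moderation is an exploratory aim, and that the documents report no moderator result. Over-reading of a null result is a risk, not something shown to have happened.

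**Conclusion.** The conflict is real but conditional. With 240 evaluable children, 60 per cell, and the same contrast, SD and alpha, Aim 3 power must be below Aim 1 power, and the stated 0.87 and above 0.90 cannot both hold. Taking SD 6 directly, Aim 3 is about 0.82 rather than above 0.90. Testing change from baseline at r = 0.6, Aim 3 is about 0.90 and Aim 1 is 0.93 to 0.95 rather than 0.87. With 240 in both aims, the readings checked here approach the stated pair only if Aim 1 is a score difference and Aim 3 a change.

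The result assumes that the 2.5 (or 2) and the 4.5 points are the same kind of quantity. The size of each power, but not the order, depends on two-sided 0.05.

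A reader might go further in two ways that the documents do not support. One is to conclude that the true Aim 3 power is 0.79. That comes from scaling 0.87 for 2.5 points and SD 6 (noncentrality 3.086 × 0.90 = 2.778, power 0.793), but direct calculation gives 0.895 for that pair, so the anchor is not reproduced. The other is to conclude that Aim 1 is underpowered, or that the Aim 3 figure is the wrong one. The calculations show no Aim 1 shortfall for either stated difference, and nothing identifies which figure is in error.

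**What to change.** Re-run both powers under one stated set-up (alpha, sidedness, tested contrast, number per cell, correlations) and replace the figures in Protocol 5.5 with the results. On the calculations above:

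- if SD 6 applies directly to the tested difference, Aim 3 becomes about 0.82, and Aim 1 about 0.90 for 2.5 points with SD 6 (0.87 for 2 points with SD 5);
- if change from baseline is tested, Aim 1 becomes about 0.95 (0.93 for 2 points with SD 5) and Aim 3 about 0.90.

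Do not insert 0.79. Give each of the two Aim 1 pairs its own power. If the aims did use different contrasts or numbers of children, state which, and do not present the two powers as comparable. State how the 5.0 units relate to the 2.5 points, or delete them.

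The cost is a few sentences and one re-run of the two simulations. Enrolment, conduct and analysis do not change. What changes is a stated power, and with it how a null moderator result should be read.

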6 SAFETY MANAGEMENT

6.1 Clinical Adverse Events

Clinical adverse events (AEs) will be monitored throughout the study.

6.2 Adverse Event Reporting

Since the study procedures are not greater than minimal risk, SAEs are not expected. If any unanticipated problems related to the research involving risks to subjects or others happen during the course of this study (including SAEs) they will be reported to the IRB in accordance with CHOP IRB SOP 408: Unanticipated Problems Involving Risks to Subjects. AEs that are not serious but that are notable and could involve risks to subjects will be summarized in narrative or other format and submitted to the IRB at the time of continuing review.

7 STUDY ADMINISTRATION

7.1 Treatment Assignment Methods

7.1.1 Randomization

Planned centrally by the investigative team's biostatistician, randomization will be stratified by practice, gender, and age groups (5-7 years old and 8-12 years old) to ensure balance. Any differences in treatment preferences between arms in the analysis will be statistically controlled

Allocation concealment (blinding of the treatment assignment) will be implemented using sealed, opaque envelopes, along with stratification, and randomly permuted blocks of unequal sizes (to prevent providers and patients from manipulating the randomization to favor any treatment). Treatment assignment will be done at the time of enrollment following informed consent

7.2 Data Collection and Management

1. Confidentiality.

To ensure confidentiality of information, data will be stripped of potential identifiers and all written and computerized files will be indexed by a unique identification number. Only research staff will have access to this information, and the PI will keep a separate master list stored as a password protected document on a password-protected computer. All databases for these study procedures will be maintained on CHOP's secure research server, and all analyses will be performed on de-identified data only. All collected study measures will be entered directly into a REDCap database. Qualitative data will be entered into an NVivo database. The unique identifiers will be used to track enrolled families over the course of the study. Audio recordings will be transcribed by ADA Transcription (http://www.adatranscription.com/). Audio recordings will be de-identified and sent via their secure server, and subsequent transcripts will be saved on a secure server accessed only by members of the study team. Confidentiality will also be maintained by use of subject code numbers in all presentations and publications. Each member of the research team, including investigators, research assistants, and stakeholder-investigators will receive appropriate training in human subjects research and patient confidentiality.

2. Security

Study data will be collected and managed using the secure web-based REDCap database at CHOP, an active participant of the REDCap consortium (Fitzmaurice, Laird, & Ware, 2011). Participants will enter outcome data using a web-based interface that supports encrypted data transfer from its origin to the database housed in a secure data center in Norristown, PA. REDCap supports a simple interface for validated data entry, audit trails for tracking data manipulation, export procedures for seamless data downloads to statistical packages, and procedures for importing data from external sources. All data management and analysis will proceed on secure data and software servers that have daily back-up, This approach will facilitate data acquisition, prevent data theft and loss, and achieve maximum protection from

unnecessary access. All participants will be provided with a unique study identifier, which will permit linking of study measures in the REDCap database. Qualitative study data will be de-identified, transcribed by ADA Transcription, and managed using the secure software NVivo. This software is designed to evaluate data such as interviews, open-ended survey responses, review patient feedback, and articles.

3. Anonymization

To ensure confidentiality of information, data will be stripped of potential identifiers and all written and computerized files will be indexed by a unique identification number. Only research staff will have access to this information, and the PI will keep a separate master list stored as a password protected document on a password-protected computer. All databases for these study procedures will be maintained on CHOP's secure research server, and all analyses will be performed on de-identified data only. A complete, cleaned, and de-identified dataset will be made available to PCORI and other investigators after all analyses have been conducted and within nine months of the end of the final year of funding. To obtain this data set, other investigators may contact the study PI who will provide a data sharing agreement. The data sharing agreement will permit the data set to be shared once an IRB protocol has been approved at the investigators' home institution and the investigators have signed a pledge to not attempt to identify individual study subjects. The data set will be made available on a CD-ROM or a secure FTP site.

7.3 Confidentiality

No identifiable data will be used for future study without first obtaining IRB approval. The investigative team will obtain a data use agreement between the provider (the PI) of the data and any recipient researchers (including others at CHOP) before sharing a limited dataset (PHI limited to dates and zip codes).

To ensure confidentiality of information, data will be stripped of potential identifiers and all written and computerized files will be indexed by a unique identification number. Only research staff will have access to this information, and the PI will keep a separate master list stored as a password protected document on a password-protected computer. All databases for these study procedures will be maintained on CHOP's secure research server, and all analyses will be performed on de-identified data only. All collected study measures will be entered directly into a REDCap database. Qualitative data will be managed on NVivo. The unique identifiers will be used to track enrolled families over the course of the study. Confidentiality will also be maintained by use of subject code numbers in all presentations and publications. Each member of the research team, including investigators, research assistants, and stakeholder-investigators will receive appropriate training in human subjects research and patient confidentiality. The identifiable information from this study will be destroyed 6 months after the results have been published.

7.4 Regulatory and Ethical Considerations

7.4.1 Data and Safety Monitoring Plan

The investigative team will evaluate for disclosures of PHI at each follow up visit from participating families and will provide reports of preliminary data to the stakeholder groups on a quarterly basis and to the CHOP IRB on a yearly basis throughout the duration of the study. Since this study is minimal risk, there are no plans for a data safety and monitoring board. In the unlikely event of an adverse outcome associated with this study protocol, it will be documented and discussed with the research group, the home physician practice office staff with parental permission, and reported to the CHOP IRB and the PCORI board, if appropriate. Any serious adverse events will be reported to the CHOP IRB within 72 hours and the PCORI board. Families will be promptly informed of any disclosures of PHI.

